## **5.5 Concomitant Medications and Procedures**

All concomitant prescription medications taken during study participation will be recorded in CRIMSON. For this protocol, a prescription medication is defined as a medication that can be prescribed only by a properly authorized/licensed clinician. Medications to be reported in CRIMSON are concomitant prescription medications, over-the-counter medications and non-prescription medications taken at the time of adverse events (all grades).

## **5.6 Prohibited Medications and Procedures**

HES medications, including but not limited to prednisone, will be allowed during the trial, but must be maintained at a constant dose beginning 1 month prior to enrollment until completion of the 12 week time point (primary endpoint assessment). Tapering or discontinuation of HES medications during this time will be permitted only in the event of drug toxicity.

Treatment with the following agents will not be permitted unless discussed with and approved by the principal investigator:

- 1) Systemic immunosuppressive medications other than HES medications initiated prior to enrollment
- 2) Xolair or other monoclonal antibodies
- 3) Investigational agents
- 4) Non-drug therapies (i.e. herbal products, alternative therapies)

## **6 Study Schedule**

All study assessments/procedures required for each study visit are summarized in [Appendix B](#) – Schedule of Procedures/Evaluations. “Windows” for the study time points are as follows: “Days”  $\pm$  2 days; “Weeks”  $\pm$  4 days, unless otherwise specified in section 6.5. The study window in the instance of the open-label extension of

benralizumab injection is to occur every 28 days +/- 7 days (since the previous injection). Blood volumes are given in [Appendix C](#).

## 6.1 Screening

Potential subjects will undergo screening assessments as part of protocol 94-I-0079. At a minimum, the following procedures will be performed within the month prior to enrollment:

- Complete medical history, including year of HES diagnosis, clinical evidence that led to the diagnosis of HES and prior/current HES therapies
- Physical examination
- Complete blood count and routine chemistries
- Serum tryptase level
- HIV 1/2 serology
- Hepatitis B and C serology
- *FIP1L1/PDGFRA* testing (if results of prior testing at NIH are not available)
- Serum or urine pregnancy test (for women of childbearing potential)
- Additional testing as clinically indicated to assess end organ manifestations

Those subjects who meet the eligibility criteria (Section 4.3) will be offered enrollment in the study.

## 6.2 Enrollment/Baseline

Signed informed consent will be obtained prior to any study procedures being performed. Baseline studies will be performed no more than 14 days prior to study drug administration and will include:

- Complete history and physical examination
- Vital signs, including weight
- CBC with differential
- Routine laboratory testing, including electrolytes, liver panel, mineral panel, LDH, CPK, uric acid, troponin, ESR, CRP, PT/PTT and urinalysis
- Serum tryptase, B12 and quantitative immunoglobulin levels (including IgE)
- HgbA1c
- Serum pregnancy testing in women of child-bearing potential
- Whole blood flow cytometry to assess eosinophil activation, IL-5R expression, basophil numbers and activation, T/B/NK cell subsets
- ECG
- Echocardiogram
- Pulmonary function testing including spirometry with bronchodilator response, evaluation of lung volumes and diffusion capacity

- Additional clinical testing as determined by pattern of clinical involvement
- Tissue biopsies of affected organs (where possible)
- Bone marrow aspirate and biopsy, including
  - quantification of eosinophils, mast cells, and their precursors
  - assessment of mast cell activation status (CD69 and CD63 surface expression)
  - assessment of IL-5R expression on eosinophils, basophils and their precursors
  - viable storage of bone marrow mononuclear cells for future studies
- T and B cell receptor rearrangement studies
- Collection of 60 cc whole blood for isolation and storage of plasma and PBMC for research studies
- Collection of serum, plasma and urine for immunologic analyses
- Measurement of benralizumab and anti-benralizumab antibody levels

### **6.3 Randomization and Blinding**

The subjects, the investigators, and all who are involved in the evaluation of the study subjects including study monitors and central laboratory personnel are blinded to a subject's treatment assignment until all subjects have completed the week 13 visit. The NIH research pharmacist is identified as the unblinded third party who will be in charge of treatment assignment, maintaining study supplies/inventory list, and preparing the blinded study medication for each subject. The NIH research pharmacist will be independent of any study assessments. To maintain blinding, any discussion of the treatment assignment between the clinicians and the pharmacy staff is prohibited until the study is unblinded.

Subjects will be assigned a screening number after completion of the eligibility checklist for enrollment in the study in CRIMSON. The study statistician or NIH research pharmacist will generate the randomization codes. These codes will be maintained by the NIH research pharmacist. To reduce the potential for participant dropouts during the period between enrollment and initial dosing of the study agent, randomization will be defined to occur on the day that the first dose of study drug is administered. A study allocation number (1 through 20) will be assigned at this time.

Because benralizumab (but not placebo) is expected to decrease peripheral and bone marrow eosinophil counts, the results of white blood cell count, peripheral eosinophil count, lymphocyte phenotyping, and bone marrow aspirate and biopsy collected after the initial dose of benralizumab or placebo until week 13 of study treatment will be blinded to the study team and subjects until all subjects have completed week 13 of the study. Results of blood tests performed after this time (week 13 until the end of the study) will not be blinded since all subjects will be receiving benralizumab and knowledge of the results would not allow the study team to determine whether the subject had received benralizumab or placebo during the double-blind portion of the study. The NIH Clinical Research Information System (CRIS) by which laboratory

results are reported does not permit blinding of selected portions of the complete blood count and differential. A qualified NIH pathologist will monitor, in real time on a day to day basis, the results of the complete blood cell count and differential (including peripheral eosinophil count) during this period and will review the results of the bone marrow performed at 12 weeks. The physician who monitors these results will not be involved in the evaluation of study subjects or in making any study assessments. The NIH physician monitoring the results will notify the study team of critical or abnormal values (for example, low absolute neutrophil counts or abnormal hemoglobin or platelet values), but this will not result in unblinding of the randomization unless the absolute eosinophil count is revealed, intentionally (if medically indicated) or unintentionally.

Subjects will be instructed to inform outside physicians that they are participating in this study and should not be informed of the results of eosinophil counts performed at an outside facility during the first 13 weeks of the study unless withholding this information compromises their medical care. The outside physician will also be contacted by the study team regarding the protocol requirements. Results or reports received from outside laboratories or physicians that could lead to unblinding of the study team will be handled by a study coordinator designated to fulfill this role. This study coordinator will not be involved in decisions pertaining to the medical management of the study subjects and will redact information that could inadvertently lead to unblinding of the study team.

### **6.3.1 Maintenance of Safety in the Face of Blinding**

Clinical management of subjects with HES is typically guided by a combination of signs and symptoms and the peripheral absolute eosinophil count (AEC). Changes in AEC in the absence of clinical manifestations would not provoke a change in therapy unless the change were dramatic (change >2 fold or AEC >5000/ $\mu$ L) and confirmed with a second CBC. In order to ensure safety of the participants, the NIH physician monitoring the counts will be instructed to notify the PI if a change of this magnitude occurs. As discussed above, the PI will be informed of all abnormal values in CBC parameters other than the AEC. Although we do not anticipate bone marrow changes at week 12 that would lead to changes in therapy, should abnormalities be detected that require therapeutic intervention, the NIH pathologist will notify the PI.

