### **6.3.2 Implications of Blinding on Safety Reporting**

As described above (Section 6.3), the study team will be blinded to the complete blood count and differential during the placebo-controlled portion of the study. It is anticipated that, during this time, some blinded laboratory values will meet the threshold of an AE. For laboratory tests other than the absolute eosinophil count, the NIH pathologist monitoring the tests in real time will inform the PI of critical or abnormal results, and these will be recorded as described in Section 11.14.4. For absolute eosinophil counts that fall outside the normal range but do not reach the threshold for breaking the blind,

reporting will be deferred until the blind has been lifted. Reporting of bone marrow abnormalities at week 12 will also be deferred until the blind is lifted except in cases where therapeutic intervention is indicated on the basis of the findings.

SAEs, and AEs of grade 3 or greater will continue to be forwarded to and assessed by the PI, and will be reported in real time, as will any events that are part of a concerning clinical picture, or that present a scenario requiring intervention.

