## 11.2 Documenting, Recording and Reporting Adverse Events

All AEs occurring from the time the informed consent is signed through the specified 1 year study follow-up period will be documented, recorded, and reported.

At each contact with the subject, information regarding AEs will be elicited by appropriate questioning and examinations and will be:

- immediately documented in the subject's medical record/source document,
- recorded in CRIMSON and
- reported as outlined below (e.g., IND Sponsor, Institutional Review Board [IRB], and Food and Drug Administration [FDA]).

If a diagnosis is clinically evident (or subsequently determined), the diagnosis rather than the individual signs and symptoms or lab abnormalities will be recorded as the AE.

A laboratory abnormality will not be reported as an adverse event if ALL of the following criteria are met:

- It is no more than "Grade 1" or "Mild" per the protocol specified toxicity table (or investigator assessment if not listed on the table); AND
- It does NOT require an intervention (e.g., discontinuation of treatment, dose reduction/delay, additional assessments, or treatment); AND
- It is assessed by the PI as NOT related to the study agent(s); AND
- It is assessed by the PI as NOT clinically significant (e.g., the abnormal value does NOT suggest a disease or organ toxicity)

All abnormal laboratory findings will be reviewed on a routine bases by the PI to identify potential safety signals. An abnormal lab not included on the toxicity table should be assessed in a similar fashion to the criteria above.

Blinded laboratories, other than absolute eosinophil counts, that meet criteria for AEs will be reported to the study team by the unblinded NIH pathologist and included in the subject's medical record and will be reported as above. Reporting of absolute eosinophil counts during the placebo-controlled portion of the study and/or bone marrow abnormalities at week 12 that meet criteria for an AE will be deferred until the blind is lifted except as specified in Section 6.3.

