#### **11.14.4 Unblinded Pathologist**

An NIH pathologist who is not involved in the clinical care of the study subjects will review all blinded CBCs and differentials obtained during the placebo-controlled portion of the study within 24 hours of the blood draw. Significant abnormalities (i.e., laboratory values that meet criteria for a grade 3 or 4 AE, SAE or that the pathologist deems clinically significant), will be reported to the PI and study coordinator immediately. Other laboratory abnormalities that represent grade 1 or 2 AEs and require no specific medical intervention, with the exception of the absolute eosinophil counts, will be reported to the PI and study coordinator in a weekly summary table.

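### The plan blinds the white cell count and the whole CBC and differential, but its reporting rules except only the absolute eosinophil count among CBC values, so an abnormal eosinophil percentage or total WBC could reach the blinded PI

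*Combined protocol and SAP*

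**What the plan says.** **What is blinded.** Section 6.3 gives its reason first: "Because benralizumab (but not placebo) is expected to decrease peripheral and bone marrow eosinophil counts". It therefore blinds "the results of white blood cell count, peripheral eosinophil count, lymphocyte phenotyping, and bone marrow aspirate and biopsy collected after the initial dose" until week 13. Section 6.3 does not name the eosinophil percentage, but section 6.3.2 brings it in by saying that "the study team will be blinded to the complete blood count and differential during the placebo-controlled portion of the study".

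**What is released to the blinded team.**
- Section 6.3.1: "the PI will be informed of all abnormal values in CBC parameters other than the AEC".
- Section 6.3.2: "For laboratory tests other than the absolute eosinophil count, the NIH pathologist monitoring the tests in real time will inform the PI" when results are critical or abnormal.
- Section 11.2: "Blinded laboratories, other than absolute eosinophil counts, that meet criteria for AEs will be reported to the study team by the unblinded NIH pathologist".
- Section 11.14.4: laboratory abnormalities that are grade 1 or 2 AEs needing no specific intervention, "with the exception of the absolute eosinophil counts, will be reported to the PI and study coordinator in a weekly summary table". Grade 3 or 4 values go to the PI and coordinator at once, and that sentence makes no exception for the AEC.

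**What else is held back.** Sections 6.3.2 and 11.2 also defer week-12 bone marrow abnormalities unless they call for intervention.

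**What counts as unblinding.** Section 6.3 says that the monitoring physician's notices do not unblind unless the AEC itself is revealed. It gives low neutrophils and abnormal hemoglobin or platelets as examples of reportable values.

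**The concern.** The blinded set and the released set overlap. Total WBC is named as blinded in section 6.3, and eosinophil percentage is blinded through section 6.3.2. Both are CBC parameters other than the AEC, so an abnormal value of either falls within the section 6.3.1 release rule.

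Eosinophil percentage is the AEC divided by the WBC, so it carries nearly the same information as the AEC. A subject whose percentage keeps appearing in the pathologist's notices probably has undepleted eosinophils. A subject whose flag disappears soon after the first dose has probably received the active drug. By section 6.5 and Appendix B, CBCs are drawn on days 1-3 and at weeks 1, 2, 3, 4, 6, 8, 10 and 12. That is 3 + 8 = 11 draws after the first dose in which such a pattern could show.

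The PI assesses AE causality (section 11.3) and the study team assesses HES signs and symptoms. Those judgements would lose the protection of the double blind.

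**Working it through.** The plan gives no figure on this point to reproduce. The check has two parts: the text, then whether the released values would identify the arm.

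**1. Text**

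| Result | Blinded by | Withheld by a reporting rule? |
|---|---|---|
| AEC | 6.3, 6.3.2 | Yes: excepted in 6.3.1, 6.3.2, 11.2 and the 11.14.4 weekly table; section 6.3.1 has its own notice for large changes |
| Week-12 bone marrow | 6.3 | Yes: deferred in 6.3.2 and 11.2 |
| Total WBC | 6.3 (named) | No |
| Eosinophil percentage | 6.3.2 (differential) | No |
| Lymphocyte phenotyping | 6.3 (named) | No: not excepted from the laboratory-test wording in 6.3.2 or 11.2 |

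**2. Direct arithmetic**

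Inputs from the protocol: entry AEC above 1000/µL (section 4.3), and a fall of at least 95% by day 7 in an earlier asthma study (section 1.1.3). Assumed: non-eosinophil WBC of 4000-8000/µL and baseline AEC of 1000-5000/µL.

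Eosinophil % = AEC / (AEC + non-eosinophil WBC).

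- Example: AEC 2000, other cells 6000. Before depletion, 2000/8000 = 25.0%. After a 95% fall, 100/6100 = 1.6%. WBC goes from 8000 to 6100, a fall of 23.8%.
- Over the whole grid, the percentage is 11.1-55.6% without depletion and 0.6-5.9% with it. The ranges do not overlap. WBC falls by 10.6-52.8%.
- With an assumed upper limit of 7%, a subject with AEC of 1000 is abnormal whenever WBC is below 1000/0.07 = 14,286/µL.

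**3. Simulation**

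All distributions are assumed: log-normal AEC truncated at 1000/µL, log-SD 0.6, medians 2000, 3000 and 5000; normal non-eosinophil WBC floored at 3000/µL; 400,000 draws per scenario. The WBC limits of 10,000 and 11,000/µL are also assumed. Entries are ranges over the three medians, plus both limits in the WBC rows.

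| Flag | Non-eosinophil WBC | Undepleted | 98% depleted | 95% depleted |
|---|---|---|---|---|
| Eosinophils >7% | 7000 ± 2000 | about 100% | 0.0-0.9% | 1-15% |
| Eosinophils >7% | 10,000 ± 3000 | 99-100% | 0.0-0.3% | 0.4-7% |
| WBC >10,000-11,000 | 7000 ± 2000 | 27-76% | 2-8% | 3-9% |
| WBC >10,000-11,000 | 10,000 ± 3000 | 68-92% | 38-52% | 39-54% |

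Eosinophil percentage separates depleted from undepleted subjects in every scenario. Total WBC does so only when the non-eosinophil count is not already high.

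**The case against.** The strongest reply is that most of the release rules are narrower than the section 6.3.1 sentence.

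- **AE filter.** Section 11.2 covers only blinded values that meet AE criteria, and the section 11.14.4 weekly table only grade 1 or 2 AEs. Section 6.3.2 introduces its rule by referring to values at the threshold of an AE. Section 11.2 also excludes grade 1 values that need no intervention, are unrelated and are not clinically significant. Section 7.1.2 speaks of newly emergent or worsening findings. A high eosinophil percentage already present at entry may pass none of these filters. Whether it can be graded at all depends on CTCAE v4.0 tables that the protocol does not reproduce.
- **Examples.** Section 6.3.1 refers back to section 6.3, whose examples are neutrophils, hemoglobin and platelets. A sensible pathologist might report only those.
- **Endpoint.** The primary endpoint is a laboratory count tested by Fisher's exact test. Section 5.6 holds HES drugs constant to week 12, with tapering or discontinuation only for drug toxicity.

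The AE filter stands for sections 11.2 and 11.14.4 and is arguable for section 6.3.2. It does not touch section 6.3.1, which covers every abnormal CBC value except the AEC. The examples are illustrations, not a closed list, and no text tells the pathologist to hold back WBC or percentages. The endpoint argument stands and limits the consequence.

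A reader might infer two stronger things. One is that the weekly table would routinely flag stable placebo subjects; the AE filter means the documents do not establish that. The other is that the primary comparison is compromised; a laboratory count with background therapy largely fixed does not support that.

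**Conclusion.** The contradiction is in the text and needs no simulation: results that sections 6.3 and 6.3.2 blind may be sent to the PI under section 6.3.1, and section 6.3 is wrong to treat only disclosure of the AEC as unblinding. The finding is that such values could be sent, not that they would be or were.

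If they were sent, eosinophil percentage would nearly identify the arm: abnormal in at least 99% of undepleted subjects against about 0-15% at 95-98% depletion. Total WBC is weaker evidence, ranging from 27-76% against 2-9% to 68-92% against 38-54% according to the assumed non-eosinophil WBC. These figures rest on assumed distributions and reference limits, and on depletion taken from asthma rather than HES.

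The exposure is to AE causality and HES symptom assessment, both secondary. The point should be corrected, but it does not invalidate the primary analysis.

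**What to change.** Reconcile sections 6.3, 6.3.1, 6.3.2, 11.2 and 11.14.4 as follows:

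1. Replace the differently worded AEC exceptions with one closed list of results that the pathologist may report to the blinded team before the blind is lifted, for example absolute neutrophil count, absolute lymphocyte count, hemoglobin and platelets. Refer to that list from each section.
2. State that the list excludes total WBC, eosinophil percentage, the other differential percentages and lymphocyte phenotyping.
3. Add a medical-need override for the excluded results. Its thresholds are a safety decision for the sponsor.
4. Amend section 6.3 so that disclosure of any excluded result, not only the AEC, counts as potentially unblinding.
5. Align the weekly-table template in section 11.14.4.

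If the double-blind part is already complete, the useful step is to check which WBC or percentage values went to the PI before week 13 and to report this beside the blinded-phase AE and symptom results.

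The cost is wording in five sections and a revised template, with no new tests or staff. The downside is that non-critical values of the excluded results reach the PI only after unblinding. The separate section 6.3.1 notice for AEC changes of more than two-fold is a different route, and this change does not close it.

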### **6.3.2 Implications of Blinding on Safety Reporting**

As described above (Section 6.3), the study team will be blinded to the complete blood count and differential during the placebo-controlled portion of the study. It is anticipated that, during this time, some blinded laboratory values will meet the threshold of an AE. For laboratory tests other than the absolute eosinophil count, the NIH pathologist monitoring the tests in real time will inform the PI of critical or abnormal results, and these will be recorded as described in Section 11.14.4. For absolute eosinophil counts that fall outside the normal range but do not reach the threshold for breaking the blind,

reporting will be deferred until the blind has been lifted. Reporting of bone marrow abnormalities at week 12 will also be deferred until the blind is lifted except in cases where therapeutic intervention is indicated on the basis of the findings.

SAEs, and AEs of grade 3 or greater will continue to be forwarded to and assessed by the PI, and will be reported in real time, as will any events that are part of a concerning clinical picture, or that present a scenario requiring intervention.

## **6.4 Study Phase**

Within 14 days of completion of baseline studies, subjects will begin treatment with study drug.

Benralizumab (30 mg) or placebo will be administered sc (as described in Section 5.4) in the OP11 clinic, the 5 SW Day Hospital, or the 5 SE inpatient nursing unit. Vital signs will be checked immediately prior to and at 30 minutes after the injection.

Subjects will be admitted to the inpatient ward for overnight observation following the first dose of study drug to facilitate monitoring of AEs. The inpatient stay may be extended if clinically indicated. Subjects will be seen daily (in OP11 or on the inpatient ward) for 3 days following the first dose of study drug, and then at weeks 1, 2, 3, 4, 6, 8, 10, and 12. Re-dosing of benralizumab or placebo will occur every 4 weeks for a total of 3 doses (at weeks 0, 4, and 8). Subjects who develop AEs after the first dose of study drug may be monitored during subsequent doses at the discretion of the investigator. Subjects who develop grade 3 or greater AEs that are considered by the investigator to be possibly, probably, or definitely related to study drug will promptly, and prior to subsequent dosing, be discussed in writing or verbally with a Sponsor Medical Monitor in the Clinical Safety Office.

At the 12 week visit, all subjects will receive benralizumab (30 mg) sc. Since the subjects who received placebo during the first 12 weeks of the study will be receiving their first dose of benralizumab at this visit, all subjects will be admitted to the inpatient ward for overnight observation following the first dose of study drug and followed daily (in OP11 or on the inpatient ward) for 3 days, every week for 4 weeks and then at weeks 1, 2, 3, 4, 6, 8, 10, and 12, 13, 14, and 15. Re-dosing of open-label benralizumab will occur every 4 weeks for a total of 3 doses (at weeks 12, 16 and 20), after which subjects demonstrating a clinical response will continue to receive additional doses every 4 weeks for one year. Non-responders will receive no further doses of benralizumab. Subsequent visits will occur at 4-week intervals for responders and at 12-week intervals for non-responders for the duration of the study. After a minimum of 2 years of complete response on the open-label extension, the dosing interval (and visits) may be increased to every 8 weeks (the FDA-approved dosing interval for severe eosinophilic asthma).

Subjects who have a sustained and complete reduction in eosinophilia and stable clinical signs and symptoms for  $\geq 2$  years and are on a stable dosing interval of benralizumab may be eligible to self-administer study drug monthly or every other month using the FASENRA PEN autoinjector. Subjects who self-administer benralizumab will have a CBC drawn monthly at NIH or a local laboratory. They will return to NIH for routine followup visits every 6 months. An interim visit will be scheduled if they develop clinical symptoms of HES and/or their AEC rises above  $100/\mu\text{L}$ .

Women of childbearing potential will undergo serum pregnancy testing prior to each administration of benralizumab.

At the 22 week visit, subjects who have not received tetanus immunization in the prior 5 years and have no contraindication to Tdap immunization will receive Tdap vaccine. The vaccine will be administered by a study nurse in the OP11 clinic according to standard clinical protocol (0.5 mL intramuscularly).

